## Active Movement Therapy (AMT), EMG Video Game:

The alternate session will consist of directly training muscle activation patterns by playing a computer game. A cursor, or "game piece" will be controlled by the patterns recorded from surface EMG electrodes (Bagnoli, Delsys, Inc.) positioned over a subset of the following muscles: FDS, EDC, thenar eminence, hypothenar eminence, first dorsal interosseous, flexor carpi radialis (FCR), and extensor carpi ulnaris (ECU). We will use principal component analysis (PCA) to determine basis vectors which can be used to explore the activation workspace defined by these muscle groups for each subject. Actions on the computer screen are associated with activation of specific principle components (PCs) (Fig. 5). For example, activation levels of the first and second PCs can correspond to the x- and y-coordinates for the user's game piece. Movement of the game piece can then be used to spell specific words (Fig. 5b), reveal a hidden picture (Fig. 5c), navigate a maze, or play a version of Asteroids. As the user progresses, the PCs controlling the game piece will be periodically cycled, such that the third and fourth PCs control the x- and ycoordinates, for example. Desired PCs can also be explicitly created from the graphical user interface, such as to have the user focus on activating individual muscles. If simultaneous control of 2 PCs proves too difficult, one-dimensional versions of the letter and hidden picture games can be used. Again, half of the subjects in this active training group will be concurrently taking cyproheptadine while the other half will be taking a placebo.

[figure not shown]
**Fig. 5**. Computer games to guide exploration of the activation workspace. A) EMG signals are converted into PCs in real-time to drive a computer video game. B) Control of two PCs moves the game piece (here, a red dot) along the horizontal and vertical axes to reach the indicated letter (which turns color from green to yellow when the red dot is properly positioned). C) User moves the red dot to the correct tile (highlighted in green) to remove the tile and

## Passive Stretching, VAEDA glove:

We recognize that exposure to a novel device such as the VAEDA glove and regular visits to the Coleman Hand Rehabilitation Laboratory could have a placebo effect by focusing attention on the impaired upper extremity. Thus, the comparison group, comprised of the other half of the subjects, will have similar exposure to the laboratory and device, but will not undergo active movement therapy. Instead, they will wear the VAEDA glove while it moves their digits from a flexed posture to full extension and then allows them to return to the flexed resting posture at a rate of roughly 15 cycles per minute. We have found this passive, cyclical stretching to have a transient impact on motor control, although the effects did not seem to carry over from one day to the next in individuals with chronic impairment (Triandafilou, et al., 2014). For each session, subjects will receive two 20-minute stretching sessions, with 10 minutes of rest in between. Half of this group will concurrently be taking cyproheptadine while the other half will be taking a placebo.

### Outcome Measures:

Subjects will be tested at the Arms and Hands Lab at baseline and the end of each week during the titration phase. Thus, data will be collected prior to administration of any agent, after one week at the lowest dosage of up to 8 mg per day, after one week at the next dosage of up to 16 mg per day, and after one week at the highest dosage of up to 24 mg per day. Data from the 4 testing sessions will be used to assess the impact of cyproheptadine on stroke. All outcome measures will be collected during each testing session. Pill counts will be performed each week as well to gauge subject compliance.

**Fig. 6.** Depiction of the interface between the fingers and the device. The motor shaft rotates the U-piece coupled to the proximal phalanges of the fingers. For the spasticity experiments, the proximal and distal interphalangeal joints will be fixed in neutral with finger splints.

Three potential manifestations of motoneuronal hyperexcitability will be quantified: spasticity, excessive coactivation during voluntary contraction, and prolonged muscle relaxation time. Spasticity will be precisely measured using techniques we have successfully employed in the past in which all four fingers are coupled to a servomotor through a custom jig (Fig. 6). Rotation of the servomotor shaft produces equivalent rotation of the MCP joints. The servomotor will impose constantvelocity rotation of the MCP joints in order to stretch the long finger flexors. Fast MCP rotation (300°/s) will be applied to evoke a stretch reflex. Slow MCP rotation (10°/s) will be imposed to measure nominally passive resistance. Wrist orientation and position will be fixed with a fiberglass cast which is subsequently clamped to a table (Fig. 6). MCP angle, angular velocity, and torque are recorded for analysis of spasticity. EMG recordings will be obtained with surface

electrodes (Bagnoli) from EDC and FDS. Subject strength will also be assessed, by having subjects perform maximum voluntary MCP flexion and extension in the same testing jig while the servomotor provides resistance. The EMG data recorded during these isometric contractions will be used to quantify coactivation. Finally, FDS relaxation time will be determined by having the subject create maximal grip force in the jig and then relax upon hearing the termination of an auditory tone, as we have done previously. Both upper extremities may be tested in a subset of participants in order to determine the impact of cyproheptadine on the non-paretic (ipsilesional) side.

Clinical assessments will be performed at the baseline, pretreatment (week 3), mid, post and follow up evaluation sessions by the study research therapist and study team. This battery of assessments includes the GWMFT, FMA, Chedoke McMaster Stroke Assessment – Stage of Hand (CMSA-H), grip and pinch strengths, the Modified Modified Ashworth Scale (MMAS), the Jebsen Hand Function Test, the Nine-Hole Peg Test, the Box and Blocks Test (BBT), and the Semmes Weinstein Monofilament Touch test.

In addition to these neuromechanical measurements, subjects will be evaluated in terms of sleepiness, depression, and weight gain. These are side effects that could dissuade use of the medication. The Epworth Sleepiness Scale (ESS) will be given to subjects at each testing session (Johns, 1991). This instrument consists of a self-assessment of the propensity to doze (ordinal scale, 0-3) during each of 8 activities of daily living (e.g., sitting and talking to someone). We will use the Beck Depression Inventory-II (BDI-II) for assessing depression in our subjects. The BDI-II is a self-report of 21 items rated on an ordinal scale from 0-3 (Beck, et al., 1996). The BDI-II, a revised version of the Beck Depression Inventory (Beck, et al., 1961), was developed to remove possible bias for older adults from the original instrument. Additionally, subjects will be weighed each week to track fluctuations in weight.

## DATA AND SPECIMEN BANKING: N/A

## DATA AND SPECIMEN MANAGEMENT: N/A

## PROVISIONS TO MONITOR THE DATA TO ENSURE THE SAFETY OF PARTICIPANTS:

A medical monitor will periodically evaluate the data collected regarding harms to determine whether participants remain safe. Findings from the medical monitor will be reported to the IRB during scheduled continuing reviews.

The data monitor will have access to all data collected, including side effects checklists, surveys and untoward events. This information is collected at the evaluation study visits beginning with the medical examination with the study doctor and Baseline evaluation. The data monitor will perform monitoring every 6 months for the first 1-2 years of the study, then annual if no change to the unanticipated adverse effects of this study.

## WITHDRAWAL OF PARTICIPANTS:

Non-compliance with study protocol, or if it is deemed appropriate for the subject's safety by the study doctor or PI, will result in removal from the study.

If a subject chooses to stop involvement in the study prematurely, the study doctor will be notified, and will recommend beginning the titration process for weaning the subject from the study drug. This will be handled on a case-by-case basis which would involve at least one additional visit with the study doctor.

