### PROCEDURES INVOLVED:

Study Design:

[figure not shown]
Treatment, Parallel Assignment, Double Blind (Subject, Caregiver, Investigator, Outcomes Assessor), Randomized, Efficacy Study.

Over the course of the study, subjects will participate in a therapy regimen involving either active practice of hand and arm movements or passive stretching of the digits, while concurrently receiving either cyproheptadine or placebo. Thus, the study has two experimental factors: Drug (cyproheptadine hydrochloride/placebo) and rehabilitative movement training (active/passive). Subjects will be randomly divided into four groups, stratified by initial FMA score, consisting of the four combinations of Drug and Training:

- cyproheptadine with active movement training
- placebo with active movement training

- cyproheptadine with passive stretching
- placebo with passive stretching.

Twenty-five subjects in each group will complete the study for a total of 100 participants. The therapists, other research personnel (including the PI), and the subjects will all be blinded as to which agent each subject is taking.

**Fig. 2**. Dosage and evaluation scheduling for the subjects. During the titration period, dosage is increased each week from 8 mg/day toward the target chronic dose of 24 mg/day. The 6 weeks of training will occur once the chronic dose has been established. Arrows indicate evaluation sessions.

As cyproheptadine can have side effects, the dosage is generally titrated over time to the desired chronic daily dose in order to permit accommodation to the drug. This dosing schedule can alleviate the severity of some of the side effects. For this study, both cyproheptadine and the placebo will be titrated in the same manner, beginning at up to 8 mg (up to 4 mg taken 2 times daily) and increasing the next week to up to 16 mg (up to 8 mg taken 2 times daily) and reaching the desired dose level of up to 24 mg per day (up to 8 mg taken 3 times daily) the following week (Fig. 2). If side effects occur at higher doses, but not at lower doses, the subject will be maintained at the highest dose tolerated for the remainder of the treatment phase. Participants will maintain this daily dosage for 6 weeks, during which time training will be performed. After completion of the training period, dosage levels will be reduced back to zero over a two-week period. The drug dosage may be reduced from the target level as recommended by the study doctor.

[figure not shown]

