The hospital pharmacy will dispense the allotment of the study drug to research staff at each change in dosage over the course of the study (5 dispenses). All pills will be encapsulated by the Research Pharmacist so that both cyproheptadine and placebo will be identical in appearance and weight. Only the Research Pharmacist and study Statistician will have the key identifying which drug each subject was given. In this manner all other study personnel, including the PI, and the subjects will remain blinded as to group membership until the study is complete, or the revealing of this information is deemed medically necessary. Each week during the titration period, the subject will come to the Arms and Hands lab to receive his/her weekly allotment of pills from study staff. Examination by the study doctor will occur at baseline, midpoint, and at the end of the study. To monitor type and severity of potential adverse side effects of the medications, the study doctor or a study team member will complete a checklist for each subject weekly. All subjects, even those in the placebo group, will be given this checklist. Adverse side effects will be rated as "none", "moderate", or "severe" based on subject report. If a subject feels unable to

continue the study due to any side effects, she may end her study participation at that time. Transportation can be arranged to convey subjects to and from the Shirley Ryan AbilityLab during this period in order to preclude the need for subjects to drive when they may be experiencing dizziness or somnolence from the medication. Weekly pill counts will be performed to gauge subject compliance with taking the medication. Participants will receive the subsequent allotment of pills at each dosage change.

Once the chronic dosage is attained, therapeutic training will begin for all subjects. The sensorimotor therapy, consisting of 18 one-hour sessions held over 6 weeks, will focus on the impaired upper extremity, particularly the hand.

[figure not shown]

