## **RISKS TO PARTICIPANTS:**

The primary risks for involvement in this study are associated with the pharmacological agent to be tested. Although cyproheptadine hydrochloride itself is not being used or administered differently than the FDA approved method, it is being used for a potentially different outcome, namely reduced unwanted muscle tone following stroke.

Some of the potential side effects of taking cyproheptadine include: diminished mental alertness, drowsiness, dizziness, hallucinations, insomnia, muscle weakness, chest congestion, headache, hypertension, increased appetite, upset stomach, diarrhea, difficulty urinating, vision problems, skin rash and dry mouth, nose, and throat, and convulsions. Although reported clinical experience has not identified differences in responses between the elderly and younger patients, elderly patients should be more cautious of possible risks. These risks may include decreased hepatic, renal or cardiac function.

To minimize these risks, we will begin with low levels of the drug and gradually titrate (increase) up to the optimal target dose for the study, which is still well within the safe level of this drug. Patients will be evaluated weekly and will be able to contact the study doctor at any time with questions or concerns. As a precautionary measure, liver profiles (requiring blood draws) will be run prior to initiation of drug administration and at the end of week 3 (chronic drug dose) to check drug impact on liver function although liver damage is not a known side effect. Following the medical screening, additional labs may be ordered at the discretion of the study doctor. Adverse events, including falls, will be assessed weekly at minimum.

Additionally, the medication may have side effects when combined with other types of drugs and/or alcohol. Some side effects of taking combined drugs may lead to confusion, high blood pressure, high fevers, tremor or muscle rigidity, and increased activity.

The effects of the study drug, cyproheptadine, on human sperm and eggs have not been studied and are therefore unknown. The effects of cyproheptadine in humans have not shown to cause negative conditions in either the mother or the fetus during pregnancy.

However, studies in animals have shown an increased risk of birth defects and fetal hormonal imbalances. The effects of this medication in women who are nursing have been shown to produce hormonal imbalances in the newborn.

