Although not in the FPI for cyproheptadine, risks of falls, cognitive decline and increased mortality have been associated with use of other such drugs with antihistaminic and anticholinergic effects.

There are also risks with the use of the actuated hand orthosis, the VAEDA glove, to provide extension assistance or stretching. This device, as well as the motor used during the evaluations, has the potential to cause too much stretching, which may cause pain or damage to the joint. A number of safety features, however, have been implemented to attempt to reduce these risks, such as mechanical stops and limit switches. Additionally, the subject will be monitored continuously by research staff while using this equipment.

Skin irritation could result from the use of self-adhesive surface electrodes. This will be minimized by cleaning the skin with alcohol before and after their application. In case of any incident, emergency medical services are routinely available at the Rehabilitation Institute of Chicago and at the adjacent Northwestern Memorial Hospital emergency room.

Due to the repetitive motions of the arm and hand, subjects also risk experiencing fatigue, muscle pain, or soreness.

The electrical stimulation used to measure muscle activation can cause pain; for some people it is sharp like a prick of a needle. We will use a series of stimulation pulses that we have found to be least painful. Additionally, we will carefully adjust the stimulation level to minimize discomfort.

The cast saw used to remove the fiberglass cast placed around the wrist for the evaluations could produce burns if left for too long in one place. All study personnel will be trained in the proper use of this saw.

Some questions we ask from the BDI-II examination may be upsetting or make the subject feel uncomfortable. If they do not wish to answer a question, they may skip it and go to the next question. A BDI-II total score above 13 will be reported to the study doctor immediately, and a private consultation with the study doctor arranged. Likewise, any suicidal ideations revealed through the BDI, regardless of total score, will be reported to the study doctor. In either case, the individual will be advised to seek counseling.

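### The Aim 1 ANOVA and MANOVA state no analysis set or missing-data method; in standard form they discard early leavers' data, which can hide harm on sleepiness and strength

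*Protocol*

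**What the plan says.** **Exit.** The protocol's section on withdrawal gives this rule for taking subjects off the study: "Non-compliance with study protocol, or if it is deemed appropriate for the subject's safety by the study doctor or PI, will result in removal". For a subject who chooses to stop, the section describes weaning and a study-doctor visit, but no further outcome evaluation. Under Procedures Involved, a subject who feels unable to "continue the study due to any side effects, she may end her study participation at that time". The same section limits such exits: when side effects appear only at higher doses, "the subject will be maintained at the highest dose tolerated for the remainder of the treatment phase".

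**Numbers.** Procedures Involved: "Twenty-five subjects in each group will complete the study for a total of 100 participants". Number of Local Participants repeats the target of 100 and expects to enrol 200, giving ineligibility and dropout together as the reason. The SAP power paragraph uses 50 per drug group.

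**Aim 1 data and analysis.** Outcome Measures: "Data from the 4 testing sessions will be used to assess the impact of cyproheptadine on stroke". These are baseline and the ends of weeks 1, 2 and 3. The SAP plans repeated measures ANOVA with factors Drug and Session. Spastic reflex, relaxation time and coactivation go into a MANOVA with follow-up ANOVAs; flexion strength, extension strength, ESS and BDI-II each get a separate ANOVA. The only fallback is for non-normal residuals. The SAP wants few false negatives for ESS and BDI-II, and says the numbers suffice to pick up moderate losses of strength or rises in sleepiness.

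**Side effects.** Risks to Participants: "Some of the potential side effects of taking cyproheptadine include: diminished mental alertness, drowsiness, dizziness, hallucinations, insomnia, muscle weakness". Of sleepiness, depression and weight gain, Outcome Measures says: "These are side effects that could dissuade use of the medication".

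**The concern.** Standard repeated measures ANOVA and MANOVA need a full row per subject. Someone who attends baseline and week 1 and then leaves contributes nothing, although half of that person's Aim 1 sessions were observed. The SAP does not override this.

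The loss is unlikely to be neutral for every outcome. Dose rises weekly through the Aim 1 window, so side-effect exits can fall inside it. Drowsiness is what ESS measures, and muscle weakness is close to what the strength tests measure. If the sleepier or weaker subjects on drug leave, those who remain look better than the randomised group. Aim 1 seeks reduced hyperexcitability without compromised strength, so a null result on strength or sleepiness counts in the drug's favour. A complete-case analysis could produce that null for the wrong reason, against the SAP's stated wish to avoid missing harm.

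**Working it through.** **1. The plan's own figure.** Inputs from the SAP power paragraph: N = 100, α = 0.05, effect size 0.22 (read as Cohen's f), power 80%; m = 4 sessions. The correlation is not given; ρ = 0.5 is assumed here. For the between-drug test:

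λ = f²·N·m / (1 + (m − 1)ρ) = 0.0484 × 100 × 4 / 2.5 = 7.74, df 1 and 98, power 0.787.

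Exactly 80% needs f = 0.224, so 0.22 reproduces to rounding. The formula takes all 100 subjects at all four sessions; nothing is allowed for missing sessions.

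**2. Illustration: inputs, all assumed.** Unit variance; correlation 0.7 between any two sessions; true ESS rise of 0.4 SD on drug at weeks 1 to 3; 60 randomised per arm. Exit comes after week 1, by a logistic model on the week-1 change (log-odds 0.7 per SD of change). Two versions are run: the same slope in both arms, and outcome-related exit on drug only. Dropout is 15% v 10% or 21% v 10% (drug v placebo). There are 4,000 trials per case for power.

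**3. No dropout, by formula.** The drug-minus-placebo differences (0, 0.4, 0.4, 0.4) have mean 0.3 and deviations −0.3, 0.1, 0.1, 0.1, with sum of squares 0.12. For Drug x Session:

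λ = (n/2) × 0.12 / (1 − 0.7) = 30 × 0.4 = 12, df 3 and 354, power 0.84. The simulation gives 83%.

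**4. Drug x Session power with dropout.** Ranges run from drug-only slope to same slope.

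| Dropout | Completers, exit unrelated to outcome | Completers, exit related to outcome | Likelihood model, all observed sessions |
|---|---|---|---|
| 15% v 10% | 76% | 65-74% | 82% |
| 21% v 10% | 75% | 58-68% | 81% |

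At 15% v 10%, the fall from 83% to 76% (7 points) is lost numbers; a further 2 to 11 points (76 − 74, 76 − 65) is selection. At 21% v 10% the split is 8 points and 7 to 17 points. The completers' estimated week-3 rise is 0.36-0.38 SD and 0.34-0.37 SD respectively; the likelihood model recovers 0.40.

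**5. No true effect.** With 50 completers per arm and 20,000 trials, Drug x Session Type I error is 5.2-6.5% at 15% v 10% and 5.8-8.1% at 21% v 10%. For the Drug main effect it is 4.7-5.1%. Completer bias in the week-3 change is 0.01-0.04 SD and 0.03-0.05 SD.

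**6. Limit of the remedy.** If exit depends instead on the unobserved week-3 change, week-3 bias at 21% v 10% is 0.05-0.10 SD in completers and still 0.03-0.07 SD in the likelihood model.

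The three-measure MANOVA was not simulated.

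**The case against.** **No passage says completers only.** This stands. The protocol removes subjects from the study, not from the analysis, and 50 per group in the SAP is a power input. A reader might infer a declared completer population; the documents do not support that. The supplied SAP also covers Aim 1 only and points to an Aim 2 analysis section that is not in it, where a general rule could sit. What remains is that the named methods, run in standard form, drop incomplete subjects and the supplied text does not say otherwise.

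**The reach is narrow.** This also stands. Only exits before the week-3 evaluation cost Aim 1 data. The 100 completers are completers of the whole study, a different set from subjects with all four Aim 1 sessions. The tolerated-dose rule keeps some subjects in. Nothing here can be concluded about the primary outcome (GWMFT), whose analysis is not in the supplied text.

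**The loss appears on Drug x Session only.** True. The SAP's 0.22 matches the between-drug test, and that test shows no visible loss: with 50 completers per arm its power is 38-41% under dropout against 39% without. But it averages in the baseline session, where no drug effect can exist, so it is weak for this purpose with or without dropout.

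**Sixty per arm is not in the documents.** Correct; it gives every method the same randomised subjects. With 50 per arm and no dropout, λ = 25 × 0.4 = 10 and power is 75%; with 50 completers per arm at 15% v 10% it is 63-73%. The direction is unchanged.

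**The likelihood model is tested on favourable ground.** Its assumptions hold exactly in step 4; step 6 shows what happens when missing-at-random fails.

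**Conclusion.** The point holds as a gap in the Aim 1 analysis with a practical consequence: early leavers' observed data would be lost by default, and for ESS and strength the loss can favour a finding of no harm. It should be corrected, but it does not invalidate the design.

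The size cannot be derived from the documents. Under the stated assumptions, Drug x Session power for a 0.4 SD rise in ESS falls from about 83% to 65-74% at 15% v 10% dropout and to 58-68% at 21% v 10%; the likelihood model keeps 81-82%. The correlation, exit mechanism, rates and effect are all assumed.

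Three stronger readings are not supported. First, 200 enrolled for 100 completing is not 50% dropout, because ineligibility is pooled with it. Second, serious false-positive inflation is not shown: Type I error is about 5-8% for Drug x Session and about 5% for the Drug main effect. Third, no passage links exit to reflex torque, relaxation time or coactivation, so bias in the hyperexcitability MANOVA is not demonstrated.

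**What to change.** In the SAP:

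- Replace the repeated measures ANOVAs for ESS, BDI-II and strength, and the follow-up ANOVAs on single hyperexcitability measures, with a likelihood-based mixed model. Include all randomised subjects in their assigned drug group and every observed session, and say explicitly that subjects who leave after week 3 are included.
- Base the drug effect on Drug x Session or on one named contrast.
- Run the MANOVA on the same set, for example by multiple imputation.
- Keep the complete-case analysis as a sensitivity analysis, and add one simple missing-not-at-random analysis.
- Report dropout and its reasons by arm.

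The cost is SAP wording and a little more analysis. The mixed model relies on a missing-at-random assumption, which is why the last sensitivity analysis is needed.

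Inviting subjects who have left treatment to their remaining scheduled evaluations is optional. It would reduce missing data, but each evaluation takes about two hours, includes casting and imposed stretches, and carries a $40 stipend. It also moves the question from the drug's effect while taken towards the effect of assignment. No rule on when treatment stops needs to change.
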